According to the size of this study it is justified to assume under H_0 a sufficiently close approximation of the log-rank test (48) to the normal distribution. If the z-value from the log-rank test (for the difference $S_{\text{finerenone}} - S_{\text{placebo}}$), stratified by the stratification factors (type of albuminuria, region, eGFR category) is larger than the critical quantile from the normal distribution ($z_{0.975} = 1.960$ or $z_{0.9833} = 2.128$), the null hypothesis will be rejected in favor of the alternative hypothesis.

The nominal significance levels and the critical values at the final analysis will be adjusted to account for the interim analysis, see Section 10.5 for more details.

In order to provide a point estimate of the hazard ratio and a corresponding two-sided 95% or 96.67% confidence interval, a stratified Cox proportional regression model will be used. Kaplan-Meier curves will be provided for the cumulative proportions of events by treatment groups.

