10.3.3.2 Primary efficacy variable: supportive analyses

The primary analysis of the primary efficacy variable will be repeated in the PPS as a supportive analysis. Further supportive analyses of the primary efficacy variable will be performed in the FAS and PPS.

The absolute and relative frequency of subjects with an event of the primary composite endpoint until 6, 12, 18, 24, 30 and 36 months will be displayed overall and by treatment group. The number of individual events of the primary composite endpoint until 6, 12, 18, 24, 30 and 36 months will be displayed overall and by treatment group. Frequencies will be calculated for the number of individual events of the primary composite endpoint per subject until 6, 12, 18, 24, 30 and 36 months overall and by treatment group.

Kaplan-Meier estimates (the 25th, 50th and 75th percentile) of the time to the first event of the primary composite endpoint (including 95% or 96.67% confidence interval), overall 'survival' rates at 6, 12, 18, 24, 30 and 36 months and Kaplan-Meier curves will be presented for each treatment group. These analyses will be presented in total and for each level of the stratification factors (type of albuminuria, region, eGFR category).

The censoring mechanism of subjects without an event of the primary composite endpoint at the time of analysis is assumed to be non-informative for the primary efficacy analysis. Sensitivity analyses will be performed, assessing the impact of potential informative censoring of such subjects. These will include the use of different imputation rules for considering subjects without an event of the primary composite endpoint as having an event or being censored, and will be further outlined in the SAP.

For the individual events of the primary composite endpoint, the number of events per patient year will be presented overall and by treatment group. The frequency of events per patient year for a treatment group will be calculated as the number of events observed for a treatment group (counting all events, not only the first one) divided by the sum of the days from first intake of study drug for all subjects within a treatment group and multiplied by 365.25.

An 'on-treatment' analysis will be performed, including only events occurring while taking study drug or until 30 days after stop of study drug. This analysis will be performed in the FAS.

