The weighted Bonferroni-Holm procedure which will be used for the hierarchical testing of the primary and secondary efficacy endpoints, is described in section 4.7. In order to evaluate whether finerenone is superior to placebo in prolonging the time to the first event of the primary composite endpoint, the following null hypothesis will be tested using the logrank test at the two-sided significance level given above:

$$H_0: \lambda_{\text{finerenone},k}(t) = \lambda_{\text{placebo},k}(t) \text{ for all time points } t \geq 0 \text{ and each stratum } k$$

The alternative hypothesis will be:

$$H_1: \lambda_{\text{finerenone},k}(t) \neq \lambda_{\text{placebo},k}(t) \text{ for at least one time point } t \geq 0 \text{ and at least one stratum } k,$$

where $\lambda_{\text{finerenone},k}$ denotes the hazard rate of the finerenone treatment group in stratum k and $\lambda_{\text{placebo},k}$ denotes the hazard rate of the placebo treatment group in stratum k . In this context, the hazard rate is defined as the instantaneous risk of a primary composite event at a given time point provided that no such event has yet taken place. The test statistic of the stratified logrank test compares the observed number of events with the number of events expected under the null hypothesis H_0 in each treatment group per stratum.

The following decision rule to test the null hypothesis will be applied. According to the size of this study and the expected number of events, it is justified to assume under H_0 a sufficiently close approximation of the logrank test (see reference 4) to the normal

distribution. If the logrank test statistic (i.e. the standardized difference of the observed number of events and expected number of events stratified by the stratification factors region, type of albuminuria and eGFR category) is larger than the critical quantile from the normal distribution, the null hypothesis will be rejected in favor of the alternative hypothesis.

The nominal significance levels and the critical values at the final analysis will be adjusted to account for the interim analysis, see section 4.7 for more details.

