In order to provide a point estimate of the hazard ratio and a corresponding two-sided 95% confidence interval, a stratified Cox proportional hazard regression model will be used. The stratification variables will be included in the STRATA statement in SAS PROC PHREG, which will assume proportional hazards for each level of one particular stratification factor.

Kaplan Meier curves will be provided for the cumulative incidence risk of outcome events by treatment groups.

To derive the logrank test statistic and the corresponding p-value, SAS program code corresponding to the following will be used:

```
PROC LIFETEST DATA = <dataset> ALPHA=0.05 METHOD=KM;
  TIME ttevalue * ttecnsr(1);
  STRATA {stratumn} / GROUP=trtgrpnr TEST=(logrank);
RUN;

/*
where
dataset = name of sub-dataset including all ITT subjects
randomized
trtgrpnr = variable coding randomized treatment group
ttevalue = time to first occurrence of primary efficacy
outcome event
ttecnsr = censoring index (1 = right-censored, 0 = event)
stratumn = variables for stratification factors
*/
```

For the Cox proportional hazard regression SAS program code corresponding to the following will be used:

```
PROC PHREG DATA = <dataset>;
  MODEL ttevalue * ttecnsr(1) = trtgrpnr / RL TIES=EFRON
ALPHA=0.05;
  STRATA {stratumn};
RUN;
```

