6.2.1.2 Primary efficacy variable: supportive analysis

The primary analysis of the primary efficacy variable will be repeated in the PPS as a supportive analysis. For the PPS analysis, the censoring rules for the primary analysis

specified in Section 6.2.1.1 will be further restricted to events occurring up to 30 days after last study drug intake.

Accordingly, subjects with censoring or event date more than 30 days after last study drug intake in the primary analysis will be censored at the date of last study drug intake +30 days.

The following supportive analyses of the primary efficacy variable will be performed in the FAS and PPS unless specified otherwise.

The originally planned presentation of absolute and relative frequency of subjects with an event of the primary composite endpoint will be superseded by the Kaplan-Meier estimates described below.

Kaplan-Meier estimates of the time to the first event of the primary composite endpoint (including 95% confidence interval, calculated based on a normal approximation and using the Greenwood formula for the standard deviation [4]), overall survival rates at appropriate time points and Kaplan-Meier curves will be presented for each treatment group. In this context, “survival” means no event of the respective primary efficacy endpoint. These analyses will be presented in total and for each level of the stratification factors.

For the primary composite endpoint and the individual events, the incidence rate per 100 patient-years will be presented by treatment group, which is defined as the number of subjects with an event divided by the time a patient is at risk for the respective event, i.e. either the time from randomization until the first event or the censoring time, multiplied by 365.25*100. Kaplan-Meier plots, logrank tests and Cox proportional hazards regression for the time to first event of the individual components will also be provided as part of exploratory efficacy (see section 6.2.3).

An ‘*on-treatment*’ analysis will also be performed, repeating the inferential statistics (stratified logrank test and stratified Cox regression model) on the FAS. For the on-treatment analysis, as described for the PPS analysis above, the censoring rules for the primary analysis will be adapted by further restricting to events occurring up to 30 days after last study drug intake.

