The logrank test as well as the Cox regression model will also be performed without including stratification factors. The plausibility of the proportional hazards assumption will be assessed by visually examining the plot of the log of the negative log of Kaplan-Meier estimates of the survival function versus log time for evidence of non-parallelism, and by including a treatment by log-transformed time interaction into the Cox model. For the latter, the SAS code is adapted as follows:

```
PROC PHREG DATA = <dataset>;  
  MODEL ttevalue * ttecnsr(1) = trtgrpn trtotime / RL  
  TIES=EFRON ALPHA=0.05;  
  STRATA {stratum};  
  trtotime = trtgrpn*log(ttevalue);  
RUN;
```

The significance of the interaction will be tested at the 5% type I error level. If the interaction is significant and there is strong evidence of non-proportionality from the plots, time-dependent hazard ratios will be estimated with the model that includes the interaction term.

The censoring mechanism of subjects without an event of the primary composite endpoint at the time of analysis is assumed to be non-informative for the primary efficacy analysis. This also implies that the primary analysis is valid under a missing at random (MAR) assumption. Sensitivity analyses will be performed, assessing the impact of a potential informative censoring of subjects lost to follow-up or with withdrawn consent. Non-renal deaths will be treated as censored observations as in the primary analysis.

A summary of the amount of missing data by treatment arm will be given, including number of subjects who have incomplete follow-up on the respective endpoint.

Robustness with respect to missing data will be investigated with a tipping point analysis on the FAS (based on the ITT approach). The analysis will:

- Estimate the hazard at time of loss to follow-up, using a Weibull survival model fitted to the population of subjects who prematurely discontinued study treatment and adjusted for treatment group and stratification factors.
- Inflate the hazard only in the finerenone group by a known factor; assumes non-informative censoring in the control group.
- Impute events to the end of the study 1000 times, calculate the hazard ratios with the stratified Cox model specified in section 6.2.1.1 and combine them using standard multiple imputation combining rules.

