- Increase the inflation factor until upper limit of two-sided confidence interval for the hazard ratio crosses 1.0; this will be the “tipping point”. The actual confidence level of the above mentioned confidence interval will depend on whether the study is stopped for overwhelming efficacy at the interim analysis or not, and on the p-value of the primary analysis of the key secondary endpoint. The confidence intervals will be as follows:
 - At the interim analysis: Use two-sided 99.73% confidence interval
 - At the final analysis:
 - p-value of primary analysis of key secondary endpoint < 0.01576184 :
Use two-sided 95.032612% confidence interval
 - p-value of primary analysis of key secondary endpoint ≥ 0.01576184 :
Use two-sided 96.717305% confidence interval

The tipping point will show how much higher the event risk after drop-out would need to be in the finerenone group so that statistical significance is lost. Since there is no particular reason to assume that the event rate should be higher, a large tipping point will indicate robustness of the study results. Technical details of the model are provided in section 9.1.

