Modification 11: Description of primary analyses for the primary and secondary efficacy time-to-event variables

Rationale: The description of the hypotheses was made more accurate by adequately taking into account the stratification factors. At the same time, survival rates were exchanged with hazard rates to create an obvious link from the hypothesis to the hazard ratio which is given as the primary output of the Cox model. However, this exchange has no impact on the content, as survival rates and hazard rates can be translated into each other and the hypotheses of equality of survival rates and of equality of the hazard rates (per stratum) are thus equivalent. Furthermore, the SAS code for the Cox model was corrected to the stratified Cox model specified in the text (by means of adding the stratification factors to the STRATA statement).

Sections affected:

- Section 6.2.1.1: Primary efficacy variable: primary analysis

Modification 12: Modifications and additions to the sensitivity analyses for the primary and secondary efficacy variables

Rationale: The analysis of number of (recurrent) events per 100 patient-years was replaced by an analysis of incidence rate, no longer considering recurrent events because this is not meaningful for the clinical events in this study as most of them usually do not happen more than once. An on-treatment analysis was added for the FAS in line with the protocol. Further supportive analyses were added to check the proportional hazards assumption for the Cox model (plot of the log of the negative of Kaplan-Meier estimates versus log time and Cox model including treatment by log-transformed time as an interaction). More details were given for the tipping point analysis, and it was clarified that this analysis and the newly added on-treatment analysis will only be done for the primary and key secondary renal endpoint based on the FAS.

Sections affected:

- Section 6.2.1.2: Primary efficacy variable: supportive analysis
- Section 6.2.2.2: Secondary efficacy variables: supportive analysis
- Section 9.1: Appendix A: Technical details missing data imputation model for time to event

Modification 13: Censoring rules for on-treatment/PPS analysis of key renal endpoint

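### Does the primary hazard ratio need a confidence interval at the test level instead of the SAP's fixed 95%?

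*SAP*

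**What the plan says.** Protocol 10.3.3.1 asks for a hazard ratio with "a corresponding two-sided 95% or 96.67% confidence interval, a stratified Cox proportional regression model will be used". Protocol 10.3.3.2 uses the same pair of levels for the Kaplan-Meier estimates: "of the time to the first event of the primary composite endpoint (including 95% or 96.67% confidence interval". Neither section says when each level applies. The natural reading is that 96.67% goes with the 3.333% test and 95% with the 5% test.

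The SAP keeps only one level. Section 6.2.1.1 reads "In order to provide a point estimate of the hazard ratio and a corresponding two-sided 95% confidence interval, a stratified Cox proportional hazard regression", with alpha set to 0.05 in the PHREG code. Section 6.2.1.2 describes the Kaplan-Meier estimates as "including 95% confidence interval, calculated based on a normal approximation and using the Greenwood formula for the standard deviation".

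SAP 4.7 tests the primary endpoint at 0.03282695, or at 0.04967388 if the CV endpoint has a p-value of at most 0.01576184. After an early stop for success the level is 0.270%. The decision itself is tied to the logrank statistic: if it "is larger than the critical quantile from the normal distribution, the null hypothesis will be rejected in favor of the alternative hypothesis".

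The tipping-point analysis in SAP 6.2.1.2 does use intervals at the test level, for example "Use two-sided 96.717305% confidence interval" when the CV endpoint misses its level.

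**The concern.** Three things make this look like a defect.

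- The SAP narrows what the protocol specified, and section 7 of the SAP has no entry about it. Modification 11 in section 7.1 does describe other edits to the same section, including "Furthermore, the SAS code for the Cox model was corrected to the stratified Cox model specified in the text".
- The interval and the test can disagree. When the primary endpoint is tested at 0.03282695, any p-value between that and 0.05 gives a 95% interval that excludes 1 beside a null hypothesis that is not rejected. A reader who takes the interval as the verdict would draw the wrong conclusion about the main result.
- The SAP has already worked out the matching levels and uses them in a sensitivity analysis built on the same model: "calculate the hazard ratios with the stratified Cox model specified in section 6.2.1.1 and combine them using standard multiple imputation combining rules". It looks odd that the tipping-point analysis carries a test-level interval and the headline estimate does not.

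At stake would be the reading of a borderline primary result.

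**Working it through.** **Inputs.** 1068 primary events and 90% power at two-sided 3.3333% (protocol 10.4); 1:1 allocation (protocol section 5); interim at 2/3 of events with a boundary of two-sided p < 0.00270 and the final levels (SAP 4.4 and 4.7).

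**1. The plan's own levels.** Take a bivariate normal for the interim and final statistics with correlation sqrt(2/3) and an interim bound of |z| = 3.000. Solving for the final bound gives:

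| Overall level | Recomputed final level | SAP 4.7 |
|---|---|---|
| 5% | 0.049674 | 0.04967388 |
| 3.333% | 0.032827 | 0.03282695 |
| 1.667% | 0.015761 | 0.01576184 |

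The stated levels are right. The interval that matches a test at 0.03282695 is 100 × (1 − 0.03282695) = 96.717305%, the figure in SAP 6.2.1.2. The protocol's 96.67% leaves out the interim adjustment, so it would not match the final test exactly either.

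**2. Where interval and test disagree.** SE(log HR) = 2/sqrt(1068) = 0.0612.

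- The 95% interval excludes 1 if the observed HR is below exp(−1.9600 × 0.0612) = 0.8870.
- The test at 0.03282695 rejects if the observed HR is at or below exp(−2.1342 × 0.0612) = 0.8776.
- The discordant band is therefore about 0.878 to 0.887.

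Example at HR 0.88: z = 0.1278/0.0612 = 2.089 and p = 0.0367. The 95% interval is 0.781 to 0.992 and the 96.717305% interval is 0.772 to 1.003.

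If the primary endpoint is tested at 0.04967388, rejection needs an HR of at most 0.8868 against 0.8870, which is negligible.

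**3. How likely that is.** Protocol 10.4 expects treatment discontinuation to pull the observed hazard ratio above 0.80. The effective value that gives 90% power at 3.3333% with 1068 events is exp(−(2.128 + 1.2816) × 0.0612) = 0.812.

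The chance that the primary statistic falls in the band is P(1.9600 < Z < 2.1342), where Z has mean −ln(HR)/0.0612 and unit variance. For the mismatch to occur, the CV endpoint must also miss 0.01576184 (z below 2.4144). The documents give no CV hazard ratio or event count, so the last column assumes CV HR 0.80 to 0.90, 500 to 1000 CV events and independent tests.

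| True primary HR | Chance of the band (upper bound) | Chance of the band and CV missing its level |
|---|---|---|
| 0.80 | 1.9% | 0.3% to 1.7% |
| 0.812 | 2.8% | 0.4% to 2.5% |
| 0.85 | 5.8% | 0.8% to 5.1% |
| 0.90 | 6.6% | 0.9% to 5.9% |

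The middle column needs no CV assumption. The interim look is ignored throughout.

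**4. What a second interval would alter.** It would be 2.1342/1.9600 = 1.089 times as wide on the log scale, around the same estimate. The logrank statistic, the level it is compared with, the event target and the power all stay as they are.

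**The case for a change.** The strongest case for a change is that the SAP is built on the protocol version that still carries both levels, that a changed confidence level is more than an editorial matter, and that adding the matching interval is cheap. It would also remove any suspicion that an interval level was picked after a borderline p-value was seen. The difference between the documents, the lack of an explanation and the discordant band all stand.

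Several parts of that case do not carry the weight put on them.

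- **The change log.** Sections 7.1 to 7.3 record changes from one SAP version to the next, and 7.2 and 7.3 list only major ones. Version 1.0 is not available here. If it already had 95%, there was no version change to record.
- **The reader is not left in the dark.** The interval is stated to be 95%. The sentence just before it in 6.2.1.1 says that levels and critical values are adjusted and points to section 4.7, where they are given to eight decimals. Only a word such as nominal is missing.
- **Selective choice.** The 95% level is fixed in advance in the text and the code, so no choice remains after unblinding.
- **The tipping-point analysis.** There the interval limit is itself the criterion, so it has to sit at the test level. The primary interval has no such role.
- **Kaplan-Meier estimates.** Those intervals are per arm and correspond to no hypothesis test, so no mismatch can arise.
- **A test-level interval has drawbacks.** Its level would depend on the other endpoint's p-value, it would not give simultaneous coverage under the Holm procedure, and it could still differ slightly from the logrank test.

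**Conclusion.** No change is needed. The SAP departs from the protocol's wording without saying why, and in a narrow band of results the headline 95% interval would exclude 1 without a formal rejection. Followed as written, though, the plan produces a correctly calibrated 95% interval and a decision made by the logrank test at the correct multiplicity-adjusted level. Type I error, power and the conclusion are the same with or without a second interval. After an early stop the test level is 0.270%, and the same reasoning holds: the p-value is compared with that level and the interval remains a 95% interval.

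The band is an observed hazard ratio of about 0.878 to 0.887. At the planned power the chance of landing in it is at most about 2.8%, or about 0.4% to 2.5% on the assumed CV inputs. It is larger if the true effect is weaker: up to 6.6% at a true HR of 0.90. These figures rest on exactly 1068 events, a normal approximation and no interim stop; the CV-dependent range also assumes independent tests. If a result fell in the band, the report would show the p-value against the level in SAP 4.7, and an analyst would describe the 95% interval as nominal without being told to.

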6.2 Efficacy

6.2.1 Analysis of primary efficacy variable

6.2.1.1 Primary efficacy variable: primary analysis

The primary efficacy variable is the time to first occurrence of the composite endpoint of onset of kidney failure, a sustained decrease of eGFR $\geq 40\%$ from baseline over at least 4 weeks, or renal death. All events classifying for the primary endpoint have to be adjudicated positively by an independent adjudication committee.

The primary analysis of the primary efficacy variable will be performed in the FAS.

Events for inclusion in the primary analysis will be counted from the day of randomization (planned at Visit 1) onwards until the EOS visit following the study termination decision, or until the date of EOS notification + 4 weeks, if the EOS visit has not been performed. In the event of premature discontinuation from the study with no subsequent follow-up information, renal events will be counted up to the day of the last visit when complete information on all components of the composite renal endpoint is available with an additional rule for events occurring after this visit. To account for events of kidney failure or renal death after the last eGFR is recorded at a clinic visit, such events will be included in the efficacy analysis if they occur in the period up to one day before the next planned clinic visit. This period would be a maximum of 5 months, given the next scheduled clinic visit should take place 4 months later, plus a time window for late attendance of one month. In addition, should the subject have a non-renal death in this period then the date of death will be used as the censoring date.

Randomized subjects without an event of the renal composite endpoint at the time of analysis will be censored at the date of their last visit when complete information on all components of the composite renal endpoint is available, up to and including the EOS visit (should this visit satisfy this rule), or date of non-renal death using a time window of 5 months as above if a subsequent clinic visit had been planned. Subjects without any information about the primary composite endpoint after baseline will be censored at Day 1.

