6.2.2 Analysis of secondary efficacy variables

6.2.2.1 Secondary efficacy variables: primary analysis

Secondary efficacy variables are as follows:

- Time to first occurrence of the following CV composite endpoint: cardiovascular (CV) death or non-fatal CV events (i.e. myocardial infarction, stroke, or hospitalization for HF)
- Time to all-cause mortality

- Time to all-cause hospitalization
- Change in UACR from baseline to Month 4
- Time to first occurrence of the following renal composite endpoint: onset of kidney failure, a sustained decrease in eGFR of $\geq 57\%$ from baseline over at least 4 weeks or renal death.

The primary analysis of the secondary efficacy variables will be conducted in the FAS.

See section 4.7 for the testing hierarchy for secondary endpoints and for multiplicity adjustment of significance levels.

The primary analysis of the secondary time-to-event endpoints will be conducted analogously to the primary analysis of the primary composite endpoint, with modifications to the censoring rules as the events will differ. In the event of premature termination from the study with no subsequent follow-up information, subjects without any information about the composite endpoint after baseline will be censored at Day 1, and the following censoring rules will also apply:

- CV events will be counted up to the day of withdrawal from the study or non-CV death. Randomized subjects without an event of the CV composite endpoint at the time of analysis will be censored at the date of their last contact up to and including the EOS visit or date of non-CV death.
- Hospitalization events will be counted up to the day of withdrawal from the study or death. Randomized subjects without a hospitalization event at the time of analysis will be censored at the date of their last contact up to and including the EOS visit or date of death.
- All-cause mortality will be counted up to the last date vital status could be obtained. Randomized subjects without such an event at the time of analysis will be censored at the last date vital status could be obtained up to and including the EOS visit.

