6.2.3.1 Components of primary and secondary composite endpoints

Consistent with the methods for the primary and secondary efficacy variables, components or composites of the components of the primary and secondary time-to-event endpoints (as included in the list of other exploratory efficacy variables above) will be analyzed as exploratory time-to-event variables using the stratified logrank test stratified by the stratification factors. A point estimate of the hazard ratio and a corresponding two-sided 95% confidence interval will be calculated using a stratified Cox proportional hazard regression model. Kaplan Meier curves will be provided for the cumulative proportions of events by treatment groups.

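### SAP 6.2.1.1 labels Kaplan-Meier curves as cumulative incidence while censoring non-renal deaths, so each arm's absolute risk of the primary endpoint will be overstated

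*SAP*

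**What the plan says.** The primary endpoint is kidney failure, a sustained eGFR fall of at least 40%, or renal death. Other deaths are not events. Within the 5-month window after the last complete visit, SAP 6.2.1.1 says: "should the subject have a non-renal death in this period then the date of death will be used as the censoring date". SAP 6.2.1.2 keeps this rule for the missing-data sensitivity analyses: "Non-renal deaths will be treated as censored observations as in the primary analysis".

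On presentation, SAP 6.2.1.1 says: "Kaplan Meier curves will be provided for the cumulative incidence risk of outcome events by treatment groups". The SAS code there uses METHOD=KM and a two-level indicator (event or right-censored), so a competing death has no code of its own.

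SAP 6.2.1.2 adds that "overall survival rates at appropriate time points and Kaplan-Meier curves will be presented for each treatment group". It also withdraws the tables of absolute and relative frequency of subjects "with an event of the primary composite endpoint will be superseded by the Kaplan-Meier estimates described below".

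The pattern recurs elsewhere:

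- **CV composite (SAP 6.2.2.1):** subjects without an event are "censored at the date of their last contact up to and including the EOS visit or date of non-CV death".
- **All-cause hospitalization (SAP 6.2.2.1):** subjects without an event are "censored at the date of their last contact up to and including the EOS visit or date of death".
- **Components (SAP 6.2.3.1):** "Kaplan Meier curves will be provided for the cumulative proportions of events by treatment groups".

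Neither the protocol nor the SAP mentions Aalen-Johansen or any other competing-risk estimator.

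**The concern.** Death from a non-renal cause makes a later renal event impossible. Censoring such deaths is right for the log-rank test and the Cox model, which compare cause-specific hazards. It is not right for a cumulative risk. Kaplan-Meier treats the dead patient as still able to have the event at the same rate as those who remain, so 1-KM describes a hypothetical population in which non-renal death does not occur. It can never be below the cumulative incidence, and it exceeds it as soon as events follow such deaths. The direction in each arm is therefore certain whatever the death rate.

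At stake is what readers take from the curves and the fixed-time estimates as the absolute risk in each arm. Mortality in this population is not negligible: protocol 3.3 describes it as substantially raised. Nothing else in the plan supplies the missing quantity. The rate per 100 patient-years is a rate rather than a cumulative risk, and the crude frequency tables have been dropped.

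**Working it through.** **Inputs from the documents (protocol 10.4, SAP 3).** Placebo event rate 12% per year; hazard ratio 0.80; 4690 subjects, so 2345 per arm; 33 months of uniform accrual and 44 months in total; loss to follow-up 0.7% per year; finerenone discontinuation 5% per year; 1068 events for at least 90% power at two-sided 3.3333%.

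**Assumption.** No non-renal death rate is stated. I take 1%, 3%, 5% and 8% per year, equal in the two arms.

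**The plan's own figure.** A log-rank power calculation with these inputs, in which discontinued finerenone patients revert to the placebo hazard, needs 1068.0 events for 90% power if the hazard is set equal to the annual rate, and 1070.6 if hazard = -ln(1 - rate). Under the second conversion 4690 subjects yield 1067.6 events. The stated design reproduces, so its inputs are a fair basis for what follows.

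**Formulas, constant hazards.** With event hazard h and non-renal death hazard d:

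- 1-KM at time T = 1 - exp(-hT)
- Cumulative incidence at T = h/(h + d) × [1 - exp(-(h + d)T)]

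For placebo h = -ln(0.88) = 0.1278 per year; for finerenone 0.8h, without dilution; d = -ln(1 - p).

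**36 months, 12% per year (percent; excesses taken before rounding).**

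| Non-renal death per year | Placebo 1-KM | Placebo cumulative incidence | Excess | Risk difference by KM | Risk difference by cumulative incidence |
|---|---|---|---|---|---|
| 1% | 31.85 | 31.41 | 0.45 | 5.43 | 5.36 |
| 3% | 31.85 | 30.53 | 1.32 | 5.43 | 5.22 |
| 5% | 31.85 | 29.67 | 2.18 | 5.43 | 5.08 |
| 8% | 31.85 | 28.41 | 3.45 | 5.43 | 4.88 |

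Worked line at 3%: d = 0.0305 and h + d = 0.1583, so 0.1278/0.1583 × (1 - exp(-0.4749)) = 30.5%. The finerenone arm shows the same pattern: 26.4% by 1-KM against 26.0% to 23.5%.

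**24 months.** Placebo 1-KM is 22.56%; the excess is 0.22, 0.65, 1.07 and 1.71 points.

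**Slower event rate.** SAP 3 reports that events came in more slowly than assumed, without giving the rate. At an illustrative 8% per year (h = 0.0834), the 36-month 1-KM is 22.13% and the excess is 0.32, 0.94, 1.55 and 2.45 points.

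**Scale.** The Greenwood standard error of the 36-month placebo estimate, with 2345 per arm and the planned accrual and loss, is 1.27 to 1.37 points across the four death rates. The share of subjects who could reach t months is (44 - t)/33: 61% at 24 months and 24% at 36.

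**Risk difference.** The plan names none. One derived from the 36-month curves is 0.07 to 0.55 points too large when death is equally frequent in both arms. The sign of that bias reverses once the finerenone-to-placebo ratio of non-renal death hazards passes 1.19 to 1.24 (over death rates of 1% to 8%, 24 to 36 months, and event rates of 8% to 12%).

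**Simulation.** With staggered entry, the 36-month placebo 1-KM was 31.9% to 32.1%, and Aalen-Johansen gave 31.6%, 30.6%, 29.9% and 28.8% at the four death rates.

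**The case against.** The best counter-argument is that this is a labelling slip in a descriptive display. The phrase cumulative incidence risk occurs only in SAP 6.2.1.1. Protocol 10.3.3.1 and SAP 6.2.3.1 speak of cumulative proportions, and SAP 6.2.1.2 defines survival as freedom from the endpoint and declares its censoring assumption. Under those rules 1-KM is a recognised net-risk quantity, and relabelling would make the display honest. No confirmatory decision changes. Part of this stands: the net risk can be defended as a choice of target. The SAP does not state that choice, however, and its label names the other quantity. Relabelling alone would also leave the report with no estimate of the real-world risk.

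The plan also analyses CV death, non-CV non-renal death and all-cause mortality, and it includes an exploratory composite in which CV death is an event. These show how often patients die but correct no curve. Fixed-time crude proportions under staggered entry would not have been cumulative incidence either, so dropping them matters less than it first appears.

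The size rests on an assumed death rate, and nothing in the documents supports the 8% upper end. At an 8% event rate and 3% to 5% death, the 36-month excess is 0.9 to 1.5 points, close to one standard error. That is a fair limit on the size; it does not affect the direction.

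Finally, the arithmetic treats every non-renal death as competing, whereas the fix counts only those inside the SAP's 5-month window. The correction would therefore remove somewhat less than the computed excess.

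**Conclusion.** The concern holds. Followed as written, the SAP will report Kaplan-Meier complements as cumulative incidence and overstate the absolute risk of the primary endpoint in both arms; the event-free rates in 6.2.1.2 will be correspondingly too low as real-world probabilities. The direction is certain. The size depends on a death rate the documents do not give: about 0.4 to 3.4 points on a 36-month placebo risk of 31.9% for 1% to 8% per year, most plausibly read at the 3% to 5% assumption as 1.3 to 2.2 points, and less at 24 months or at a lower event rate. These figures assume constant hazards and equal death rates by arm.

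The same construction affects the curves for the 57% renal composite, the CV composite, all-cause hospitalization and the single components. I give no figures there because the current text states no planning rates for them. The log-rank tests, Cox hazard ratios, incidence rates per patient-year and the event target stand. This should be corrected, but it does not threaten the confirmatory conclusions.

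**What to change.** In SAP 6.2.1.1 and 6.2.1.2, estimate the curves and fixed-time risks by Aalen-Johansen with non-renal death as the competing event, and replace the Greenwood intervals with the variance that belongs to that estimator. Count a non-renal death as competing only where SAP 6.2.1.1 already uses the death date, that is, within the 5-month window. Leave later deaths censored at the last complete visit, so that the risk set matches the primary analysis.

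In SAP 6.2.2 and 6.2.3.1 apply one rule: the competing event is any death that is not itself an event of that endpoint. This means non-renal death for the 57% composite, non-CV death for the CV composite, any death for hospitalization, and for a single component any death that is not that component. Keep Kaplan-Meier for all-cause mortality. Label any other Kaplan-Meier curve that is retained as '1-KM, competing deaths censored'. Leave the log-rank and Cox analyses alone.

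The cost is SAP wording, one three-level status variable per endpoint (event, competing death, censored) and a separate PROC LIFETEST call with EVENTCODE. No new data are needed, because the Clinical Event Committee already classifies all deaths (protocol 13.1.2). The reported absolute risks will be slightly lower.
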